8.4.4 EQ-5D-5L

The EQ-5D-5L was introduced by the EuroQoL Group in 2009 and is a multi-attribute instrument used in assessing the health-related quality of life**Error! Reference source not found.**^{12,13}

The EQ-5D-5L descriptive system contains five dimensions: mobility, self-care, usual activities, pain/discomfort, and anxiety/depression. Each dimension has five levels: 1 = no problems, 2 = slight problems, 3 = moderate problems, 4 = severe problems, and 5 = extreme problems. The responses to the five dimensions will be converted into a five-digit number (eg 23245) that describes the participant’s ‘health state’. This reflects how good or bad the health state is according to the preferences of the general population of a country/region.

In order to convert the health state to a continuous health index value, value sets (ie weights ranging from 1 for a health state of 11111 to negative values for health states reflective of a poor condition such as 55555) will be utilised.

A position statement from NICE suggests to not use the EQ-5D-5L value set for England published by Devlin et al. 2018.¹⁴ The recommendation is to utilise the Van Hout cross-walk in order to obtain values for the EQ-5D-5L by mapping to the available EQ-5D-3L value sets.¹⁵ SAS code is available to carry out the cross-walk method on the United Kingdom value set on the EQ-5D website.¹⁶

If a component of the EQ-5D-5L was not collected, the five-digit health state will be recorded with ‘-’ to identify these missing values (eg 132-1, implying that the pain/discomfort item was missing) and the continuous health index value will not be derived and set to missing for analysis purposes.

The EQ-5D-5L data will be obtained at Baseline, Week 4, and Week 12 (Visits 2, 7, and 10, respectively).

8.4.5 Perceived Ability to Cope with Trauma (PACT) Scale

The PACT scale is a self-reported, 20 items scale, organised in two sub-scales, (1) Forward focus and (2) Trauma focus. The first subscale measures the ability of the individual to move beyond their trauma, while the second measures the perceived ability to focus on processing the trauma. Overall the scales provides a quantification of the individual's coping flexibility.¹⁷

Participants will complete the assessment scoring their ability to complete each item following a potentially traumatic event if they needed to on a 7-point Likert scale where 1 = not at all able, and 7 = extremely able. The subscale scores are derived by taking the mean of the items in Table 12.

Table 12: PACT Item Mapping to Subscales

Subscale	Items
Forward Focus	1, 2, 3, 4, 5, 8, 9, 13, 15, 16, 17, 18
Trauma Focus	6, 7, 10, 11, 12, 14, 19, 20

Additionally, an overall flexibility score can be derived as follows:

$$(FF + TF) - |FF - TF|$$

Where *FF* is the forward focus subscale score, *TF* is the trauma focus subscale score, and $|FF - TF|$ is the absolute difference of the scores.

8.4.6 Resilience Adult Scale (RAS)

The RAS was developed to capture a set of fundamental protective factors based on resilience research. It includes 33 items, assessed on a 7-point Likert scale where 1 is low and 7 is high, split into 6 subscales.¹⁸

The RAS data will be obtained at Baseline, Week 4, and Week 12 (Visits 2, 7, and 10, respectively).

8.4.7 Five-Dimensional Altered States of Consciousness (5D-ASC)

The 5D-ASC measures the acute drug effects using five primary dimensions and respective subdimensions to assess alterations in mood, perception, and experience of self in relation to environment and thought disorder. The five dimensions include oceanic boundlessness, anxious ego dissolution, visual restructuralization, auditory alterations, and reduction of vigilance. In addition to these five dimensions, the 5D-ASC can be split into 11 subscales, as described by Studerus et al.²⁰: experience of unity, spiritual experience, blissful state, insightfulness, disembodyment, impaired control and cognition, anxiety, complex imagery, elementary imagery, audio-visual synesthesia and changed meaning of percepts.

Participants are instructed to respond to the described experiences by placing vertical marks on a horizontal VAS 100 millimetres long. The VAS of the altered states of

consciousness rating scales are anchored as “No, not more than usual” on the left and as “Yes, much more than usual” on the right. The items are scored by measuring the millimetres from the low end of the scale to the participant’s mark (integers from 0–100). Because the low end of the scale indicates a neutral response, the response format of these items can be considered as strictly unipolar according to the response format typology of Russell and Carroll.²¹

The mapping of individual items to the five dimensions is displayed in Table 13 below (the former accounts for 93 out of 94 individual items [item 66 is excluded]).²²

Table 13: 5D-ASC Dimensions

Dimension	Items
Oceanic Boundlessness	1, 3, 9, 12, 16, 18, 26, 34, 35, 36, 40, 41, 42, 45, 50, 52, 57, 62, 63, 69, 71, 73, 81, 86, 87, 91, 94
Anxious Ego Dissolution	6, 8, 21, 27, 32, 38, 43, 44, 46, 47, 53, 56, 60, 64, 67, 78, 79, 80, 85, 88, 89
Visual Restructuralization	7, 14, 20, 22, 23, 28, 31, 33, 39, 54, 58, 70, 72, 75, 77, 82, 83, 90
Auditory Alterations	4, 5, 11, 13, 19, 25, 30, 48, 49, 55, 65, 74, 76, 92, 93
Reduction of Vigilance	2, 10, 15, 17, 24, 29, 37, 51, 59, 61, 68, 84

The overall score for each dimension is obtained by averaging the score for each individual item within that dimension.

The 5D-ASC data will be obtained at the end of the COMP360 administration session on Day 1 (Visit 3).

8.4.8 *Emotional Breakthrough Inventory (EBI)*

The EBI is an eight-item brief measure intended to index the degree to which an individual experiences their emotion during the COMP360 administration session. Each item is a VAS, with units from 0 to 100. A total score is obtained by averaging the following six items: Item 1: I faced emotionally difficult feelings that I usually push aside; Item 2: I experienced a resolution of a personal conflict/trauma; Item 3: I felt able to explore challenging emotions and memories; Item 5: I had an emotional breakthrough; Item 6: I was able to get a sense of closure on an emotional problem; Item 8: I achieved an emotional release followed by a sense of relief.²³ The other two items (Item 4: I was resisting and avoiding challenging feelings throughout, without a breakthrough; and Item 7: I felt emotionally stuck throughout, without a breakthrough) will be listed only.

The EBI data will be obtained the day after COMP360 administration on Day 2 (Visit 4).

9 STUDY PARTICIPANTS

9.1 Disposition of Participants

The summaries will be presented overall.

The number of participants screened, screen failures, and the number and percentage of participants in each analysis set will be summarised by country and overall, for the Screening Analysis Set (*Table 14.1.1.1*). The number and percentage of participants who completed the study and number and percentage of participants who discontinued from the study, with reasons for discontinuation, will be summarised using the Safety Analysis Set (*Table 14.1.1.2*). The reasons for screen failures will also be tabulated (*Table 14.1.1.3*).

Participant disposition will be listed by study discontinuations (*Listing 16.2.1.1*) and completers (*Listing 16.2.1.2*) using the Safety Analysis Set. Participation in each defined analysis set will be listed using the Screening Analysis Set (*Listing 16.2.3*). Inclusion criteria not met/exclusion criteria met at Screening and at Baseline will be listed using the Screening Analysis Set (*Listing 16.2.4.4* and *Listing 16.2.4.5*).

9.2 Protocol Deviations

The frequency and percentage of participants in each important protocol deviation category will be summarised and presented overall using the Safety Analysis Set (*Table 14.1.1.4*).

All important protocol deviations will be listed using the Safety Analysis Set (*Listing 16.2.2.1*).

9.3 Demographic and Baseline Characteristics

The Safety Analysis Set will be used for all demographic and baseline characteristics-related evaluations, unless otherwise specified. The summaries will be presented overall.

Demographic and baseline characteristics (age [years; continuous and by age categories (see Section 8.2.2)], sex [male, female], ethnicity [Hispanic or Latino, Not Hispanic or Latino], race [White, Black or African American, Asian, American Indian or Alaska Native, Native Hawaiian or Other Pacific Islander, Other], lifetime prior psilocybin experience [yes, no], height [cm], weight [kg], BMI [kg/m²; continuous and by BMI categories (see Section 8.2.3)]) will be summarised (*Table 14.1.2*).

Other baseline characteristics (duration of PTSD in months, CAPS-5 total symptom severity score, PTSD subtype [dissociative symptoms, delayed onset (see Section 8.4.1.2)], index event as collected on the CAPS-5 (see Section 8.4.1.3), and ‘how long ago did worst event happen’ as collected on the LEC-5) will be summarised (*Table 14.1.3.8*).

The MINI version 7.0.2 will be summarised (*Table 14.1.3.9*) – note this summary will only display whether participants meet the criteria for specific modules as displayed on the questionnaire cover pages.

The MSI-BPD, LEC-5, and CTQ will be listed (*Listing 16.2.9.4*, *Listing 16.2.9.5*, and *Listing 16.2.9.6*).

Listings of the demographic baseline characteristics, other baseline characteristics, and the MINI version 7.0.2 will be presented (*Listing 16.2.4.1*, *Listing 16.2.4.2*, and *Listing 16.2.9.1*).

Other Baseline measurements (Urine Drug Screen and Pregnancy Test) will be listed only (*Listing 16.2.8.5* and *Listing 16.2.8.6*). The pregnancy test listing will include results from both the urine test and, where this was done, of the serum test.

9.4 Medical History

Medical history collected at Screening will be summarised by primary system organ class (SOC) sorted by alphabetical order and by total descending frequency for preferred term (PT), and presented overall using the Safety Analysis Set (*Table 14.1.3.1*). This includes both the number and percentage of participants with a given medical history item as well as the number of occurrences of such item. In case of a tie for the number of participants with a given PT, PTs will be sorted also by the number of occurrences of that PT.

All medical history data will be listed using the Safety Analysis Set (*Listing 16.2.4.3*).

9.5 Prior and Concomitant Medications

The Safety Analysis Set will be used for all prior and concomitant medication-related evaluations, unless otherwise specified. The summaries will be presented overall. They will be sorted by alphabetical order for anatomical therapeutic chemical (ATC) level and descending frequency for PT.

Prior and concomitant medications will be summarised (*Table 14.1.3.2* and *Table 14.1.3.3*) and listed (*Listing 16.2.4.6* and *Listing 16.2.4.7*).

9.6 Prior and Concomitant Non-Drug Therapies

The Safety Analysis Set will be used for all prior and concomitant non-drug therapies (eg cognitive psychotherapy, group psychotherapy) evaluations. They will be sorted by alphabetical order for SOC and by total descending frequency for PT.

Prior and concomitant non-drug therapies will be summarised (*Table 14.1.3.4* and *Table 14.1.3.5*) and listed (*Listing 16.2.4.8* and *Listing 16.2.4.9*).

9.6.1 Prior Non-Drug Therapies for PTSD

Prior non-drug therapies for PTSD will be summarised (*Table 14.1.3.6*) and listed (*Listing 16.2.4.10*).

9.6.2 *Concomitant Non-Drug Therapies for PTSD*

Concomitant non-drug therapies for PTSD will be summarised (*Table 14.1.3.7*) and listed (*Listing 16.2.4.11*).

9.7 Treatment Exposure/Compliance and Duration

COMP360 administration will be listed (*Listing 16.2.5*).

10 SAFETY

10.1 Adverse Events (AEs)

An overall summary of AEs, including total number of TEAEs and treatment-emergent serious adverse events (TESAEs), severe TEAEs, AESIs, TEAEs and TESAEs leading to study discontinuation, and TEAEs leading to death will be presented (*Table 14.3.1.1*).

The following summary tables will be summarised by SOC and PT, and sorted by alphabetical order for SOC and by total descending frequency for PT, including both the number of participants with a given event and the number of events.

- Summary of TEAEs (*Table 14.3.1.2*)
- Summary of non-serious TEAEs $\geq 5\%$ (PT for any treatment group $\geq 5\%$) (*Table 14.3.1.3*)
- Summary of TEAEs by worst severity (mild/moderate/severe) (*Table 14.3.1.4*)
- Summary of TEAEs by strongest relationship to COMP360 (related/not related) (*Table 14.3.1.5*)
- Summary of TEAEs by time of onset (see Section 8.3.1 for categories) and duration (see Section 8.3.1 for categories) (*Table 14.3.1.6*)
- Summary of TESAEs (*Table 14.3.1.7*)
- Summary of TESAEs by time of onset (see Section 8.3.1 for categories) and duration (see Section 8.3.1 for categories) (*Table 14.3.1.8*)
- Summary of AESIs (*Table 14.3.1.9*)
- Summary of AESIs by time of onset (see Section 8.3.1 for categories) and duration (see Section 8.3.1 for categories) (*Table 14.3.1.10*)
- Summary of TEAEs leading to study withdrawal (*Table 14.3.1.11*)
- Summary of pre-treatment AEs (*Table 14.3.1.14*)

For each of the summaries done at the participant level, multiple occurrences of the same event within a participant will be counted once in the summaries by SOC and PT; multiple occurrences of the same event within a participant will be counted once in the worst severity category (severe $>$ moderate $>$ mild) and/or strongest study drug relationship category (related $>$ not related). For relationship category, related also includes “possibly related” events. If severity or relationship is found to be missing, the most severe occurrence will be imputed for that particular summary.

These summaries will also present the number of events that occurred, so multiple occurrences of the same event within a participant will all be accounted for in the worse severity category and strongest relationship category they were classed as. As an example, should a participant have two mild and three severe AEs, only these latter will be reported in the 'Severe' line of the table for the overall and appropriate SOC/PT summaries, whereas the two mild events will not be considered; similarly, if a participant has only mild events all of them will be reported in the appropriate 'Mild' lines of the display.

Summaries of the subset of (i) TEAES, and (ii) AESIs occurring within 24 hours of the COMP360 administration by SOC, PT, and start/stop time category since administration (see Section 8.3.1 for categories) will be produced (*Table 14.3.1.12* for TEAEs, and *Table 14.3.1.13* for AESIs).

AEs for which the end date is not available because the data is genuinely missing will be considered as ongoing for analysis purposes.

All AEs for each participant, including multiple occurrences of the same event, will be presented in full in a comprehensive listing including participant number, treatment, reported term, SOC, PT, date/time and study day when AE starts/stops, , duration (days), relationship to COMP360, severity, action taken, outcome, seriousness, whether concomitant medication started due to AE and whether the AE leads to study withdrawal (*Listing 16.2.7.1*). Listings will also be provided for participants who experience TESAEs (*Listing 16.2.7.2*), AESIs (*Listing 16.2.7.3*), AEs that led to death (*Listing 16.2.7.4*), and pre-treatment AEs (*Listing 16.2.7.5*).

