11.2 Assessment of Intensity

Each AE will be classified according to the following criteria:

Mild:	The AE does not interfere in a significant manner with the participant's normal level of functioning.
Moderate:	The AE produces some impairment of functioning but is not hazardous to the participant's health.
Severe:	The AE produces significant impairment of functioning or incapacitation and is a definite hazard to the participant's health.

Severity versus Seriousness: Severity is used to describe the intensity of a specific event while the event itself, however, may be of relatively minor medical significance (such as severe headache). This is not the same as "seriousness," which is based on participant/event outcome at the time of the event.

When changes in the intensity of an AE occur more frequently than once a day, the maximum intensity for the experience should be noted. If the intensity category changes over several days, those changes should be recorded separately (with distinct onset dates).

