14.2.2.5	Secondary Endpoint – Proportion of Clinician-Administered PTSD Scale for DSM-5 (CAPS-5) Responders Over Time – Full Analysis Set	Stat IProg	
14.2.2.6	Secondary Endpoint – Proportion of Clinician-Administered PTSD Scale for DSM-5 (CAPS-5) Remitters Over Time – Full Analysis Set	Stat IProg	14.2.2.6
14.2.3	Additional Efficacy Endpoints		
14.2.3.1	Additional Endpoint – Summary of Perceived Ability to Cope with Trauma (PACT) Scale Scores and Change from Baseline – Full Analysis Set	IProg	14.2.2.1
14.2.3.2	Additional Endpoint – Summary of Five-Dimensional Altered State of Consciousness (5D-ASC) – Full Analysis Set	IProg	
14.2.3.3	Additional Endpoint – Summary of Emotional Breakthrough Inventory (EBI) – Full Analysis Set	IProg	
14.3	Safety Data		
14.3.1	Displays of Adverse Events		
14.3.1.1	Summary of Treatment-Emergent Adverse Events (TEAEs) – Safety Analysis Set	IProg	
14.3.1.2	MedDRA Summary of Treatment-Emergent Adverse Events (TEAEs) by Primary System Organ Class and Preferred Term – Safety Analysis Set	IProg	
14.3.1.3	MedDRA Summary of Non-Serious Treatment-Emergent Adverse Events (TEAEs) with $\geq 5\%$ Incidence by Primary System Organ Class and Preferred Term – Safety Analysis Set	IProg	14.3.1.2
14.3.1.4	MedDRA Summary of Treatment-Emergent Adverse Events (TEAEs) by Primary System Organ Class, Preferred Term and Worst Severity – Safety Analysis Set	IProg	14.3.1.2
14.3.1.5	MedDRA Summary of Treatment-Emergent Adverse Events (TEAEs) by Primary System Organ Class, Preferred Term and Strongest Relationship to Study Drug – Safety Analysis Set	IProg	

Table Number	Table Title	Validation Method	Shell Number (if Repeat)
14.3.1.6	MedDRA Summary of Treatment-Emergent Adverse Events (TEAEs) by Primary System Organ Class, Preferred Term, Time of Onset and Duration of Adverse Event – Safety Analysis Set	IProg	
14.3.1.7	MedDRA Summary of Treatment-Emergent Serious Adverse Events (TESAEs) by Primary System Organ Class and Preferred Term – Safety Analysis Set	IProg	14.3.1.2
14.3.1.8	MedDRA Summary of Treatment-Emergent Serious Adverse Events (TESAEs) by Primary System Organ Class, Preferred Term, Time of Onset and Duration of Adverse Event – Safety Analysis Set	IProg	14.3.1.6
14.3.1.9	MedDRA Summary of Treatment-Emergent Adverse Events of Special Interest (AESIs) by AESI Term and Preferred Term – Safety Analysis Set	IProg	14.3.1.2

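### SAP 10.1 says the by-worst-severity TEAE table also counts the events that occurred, but its worked example, read naturally, counts 3 of 5

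*SAP*

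**What the plan says.** SAP 10.1 lists the summaries by system organ class (SOC) and preferred term (PT), among them Table 14.3.1.4. It describes them all as "including both the number of participants with a given event and the number of events". Section 16 titles Table 14.3.1.4 as a summary "by Primary System Organ Class, Preferred Term and Worst Severity".

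Two counting rules follow in 10.1.

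- **Participants:** "multiple occurrences of the same event within a participant will be counted once in the worst severity category", with severe ranked above moderate and moderate above mild.
- **Events:** "These summaries will also present the number of events that occurred". The sentence goes on to say that repeat occurrences are all accounted for in the worse severity and strongest relationship category they were classed as.

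The example after the event rule takes a participant with two mild and three severe events. Only the three severe events appear on the Severe line "for the overall and appropriate SOC/PT summaries, whereas the two mild events will not be considered". The contrasting case comes next: "if a participant has only mild events all of them will be reported in the appropriate" Mild lines.

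Protocol 13.5.2.1 has the same event sentence, using maximum in place of worse and strongest, but no example. SAP section 12 (changes from the protocol) and the post-lock addendum do not touch this rule.

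**The concern.** Counting a participant once, at the worst grade, is standard for a participant count. An event count answers a different question, namely how many events there were and at what grade. The event rule says every occurrence is accounted for, and the example then leaves two of five out.

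Adverse events are a primary endpoint. If the example is programmed as written, Tables 14.3.1.2 and 14.3.1.4 will give different event totals for the same participants, and nothing in the table title warns that the event column is incomplete. The shortfall falls only on mild and moderate events. No planned table gives the full split of events between those two grades, so a reader who wanted it would have to tally the listing.

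**Working it through.** This is direct counting, with no assumed rates.

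**Inputs.** From the SAP 10.1 example: one participant, 2 mild and 3 severe events, so k = 2 + 3 = 5 events, of which t = 3 are at the worst grade.

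**The plan's own figure.** The example reports 3 events on the Severe line and leaves out 2. Shown: t/k = 3/5 = 60%. Dropped: (k − t)/k = 2/5 = 40%.

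**Three ways to count the same participant in the overall row of Table 14.3.1.4:**

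| Rule | Mild | Moderate | Severe | Total |
|---|---|---|---|---|
| Each event at its own grade | 2 | 0 | 3 | 5 |
| All events moved to the worst grade | 0 | 0 | 5 | 5 |
| SAP example | 0 | 0 | 3 | 3 |

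Table 14.3.1.2 shows 5 events for this participant. The lead sentence could be read as either of the first two rules, and both reach 5. The example matches neither.

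**General form.** If participant i has k_i events, t_i of them at that participant's worst grade, the overall row falls short of Table 14.3.1.2 by the sum of (k_i − t_i). The shortfall is zero only if every participant's events all have one grade.

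**PT rows.** The SAP does not say whether worst grade is taken within each table row or once per participant, and the table shells are not in the documents. With the three severe events in one PT, the sum over PT rows is:

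| Where the mild events sit | Overall row | PT rows, rule per row | PT rows, rule per participant |
|---|---|---|---|
| Both in the severe events' PT | 3 | 3 | 3 |
| One in that PT, one elsewhere | 3 | 3 + 1 = 4 | 3 |
| Both in other PTs | 3 | 3 + 2 = 5 | 3 |

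The overall row is 3 throughout. Own-grade counting gives 5 throughout.

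**Split records.** Protocol 11.2 has a change of intensity over several days entered as a separate record with its own onset date. An episode that goes from mild to severe is then 2 records. Table 14.3.1.2 counts 2, since no merging rule is stated. The SAP example's rule counts 1, and own-grade counting gives 1 + 1 = 2, which agrees with Table 14.3.1.2.

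**What is unaffected.** A participant with any severe event has severe as the worst grade, so no severe event is dropped. Participant counts follow their own rule. Table 14.3.1.1 is "An overall summary of AEs, including total number of TEAEs and treatment-emergent serious adverse events (TESAEs), severe TEAEs", so mild and moderate events combined can be found as total minus severe. Listing 16.2.7.1 carries every event with its severity.

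**The case against.** **The convention is open.** The table is named for worst severity, the event sentence itself refers to the worse category, and an example is given. A programmer would know what to do. This stands as far as it goes: the rule is not hidden. It does not reconcile the rule with a statement that the table presents the events that occurred, all accounted for.

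**The example may say less than it seems.** A reader might infer that the example can only mean the mild events vanish from the table. That is too strong. The words about not considering them could attach to the Severe line alone, leaving them on a Mild line. The contrasting case of a participant with only mild events makes this unlikely, because it implies that mild events are otherwise not shown, but it does not rule it out. Under either reading the wording needs repair.

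**The rule may guard against double counting.** With split records, worst-grade counting shows a worsening episode once. The SAP does not give this reason, and Table 14.3.1.2 counts both records, so the two tables would still disagree.

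**Little hangs on it.** The study has one arm, up to 20 participants and no hypothesis tests, and correct counts can be recovered. This is accepted, and it sets the grade of the point.

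**Conclusion.** The point holds as a minor reporting error in one descriptive table. On the natural reading of SAP 10.1, the overall row of Table 14.3.1.4 shows 3 of the example's 5 events. Mild and moderate event counts would be too low, and the categories would not sum to Table 14.3.1.2, whenever a participant has mixed grades. The trial-wide shortfall cannot be sized, because the documents give no severity split.

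Three stronger conclusions might be inferred, and the documents do not support them.

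- **PT rows will exceed the overall row.** This follows only if the rule is applied row by row, which the SAP does not state.
- **Table 14.3.1.5 undercounts not-related events.** The parallel wording on strongest relationship invites this, but the example covers severity only. It is something to check.
- **Safety findings are lost or softened.** Participant counts, severe-event counts, the totals in Table 14.3.1.1 and the full listing are intact, and no safety conclusion is shown to change.

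**What to change.** **Preferred.** In SAP 10.1, keep worst-severity counting for participants. For events, place each recorded event in its own severity category, so that mild + moderate + severe equals the event total in Table 14.3.1.2. Delete the example that leaves out the two mild events. Treat records split for a change of intensity exactly as Table 14.3.1.2 does.

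**If the worst-severity event column is kept.** Footnote Table 14.3.1.4 to say that it excludes a participant's lower-severity events, state whether the rule applies per row or per participant, and remove the claim that the table presents the number of events that occurred.

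In either case, check how Table 14.3.1.5 is programmed and align it only if the same exclusion is found.

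**Cost.** The database is already locked and the existing addendum leaves 10.1 unchanged, so this needs a short further addendum. The preferred option adds minor reprogramming of Table 14.3.1.4. The alternative is a footnote and a wording change. Neither needs new data, and the study is open label, so no unblinding issue arises.
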